### **3.2 Primary Study Endpoints**

The key endpoints of this study include the assessment of safety, tolerance and efficacy of EVP1001-1. Safety and tolerance will be evaluated based on the nature and extent of AEs and injection-associated discomforts and changes in laboratory parameters, vital signs and ECG after administration of EVP1001-1. Effects, if any, of EVP1001-1 on QT/QTc intervals will be determined by comparing the intervals before and after EVP1001-1 across the full HR range for each patient, including use of individual correction of QT by RR. All subjects who receive EVP1001-1 will be included in the analyses. Pre- and post-dose results will be compared for vital signs, clinical laboratory parameters, ECG parameters and hemodynamic parameters to identify individual changes from baseline and potential systematic shifts. The presence or absence of infarcts and/or ischemic areas relative to the current clinical standard (by echo and gadolinium-based cardiac MRI) along with comparison to patient outcomes will determine efficacy.

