## **3 Study Design**

### **3.1 General Design**

Prior to entry into this study, all subjects will sign an Informed Consent and will then undergo a physical assessment including medical history, details regarding their cardiac history, prescription and over-the-counter drug review,, vital signs, electrocardiogram (ECG), evaluation of the major organ systems, hematology, serum chemistries. In addition, female subjects will undergo a serum pregnancy test.

Starting 30 minutes before the cardiac MRI scan (CMR), the subjects will take 16 mgs of ondansetron by mouth. CMR imaging will subsequently take place and then EVP1001-1 will then be administered approximately 15 minutes into the scan for contrast enhanced images. EVP1001-1 will be administered intravenously over approximately one minute. The subjects will each receive 0.28 mL/kg of EVP 1001-1. All subjects will be monitored closely from before ondansetron administration until their discharge from the imaging center. Following MEMRI, delayed-enhanced MRI(DEMRI)is performed using 0.2mmol/kg gadolinium. We will compare the two different contrast enhanced images (EVP1001-1 vs Gadolinium) in determining the viable, peri-infarct, and intra-infarct myocardial tissue.

To ensure a high-quality image, if the participant heart rate is greater than 65 bpm and regular rhythm, metoprolol will be given. If the HR is 65 and irregular, metoprolol will be given if there

are no contraindications (see table 1 below)

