#### Parameters to be Measured:

A standard physical assessment will be performed on the day of imaging (approximately 1-hour post dosing). Body temperature and respiration rate will be measured within 24 hours prior to dosing and at approximately 1- and 2-hours post dose. A standard 12-lead EKG will be performed both before and after the MR study to assure no significant EKG changes have occurred. Patient's hemodynamics will also be serially monitored. A baseline BP and HR will be performed before beginning the study. After EVP1001-1 contrast infusion, BP and HR will be measured every 2 minutes until 10 minutes post EVP1001-1 contrast infusion after which point a BP and HR will be measured every 5 minutes until the conclusion of the MEMRI and every 10 minutes until the conclusion of DEMRI study. There will be a 5-minute post administration observation interval outside the scanner. The patient will also have continuous EKG monitoring during this time. After the study, the patient will have another standard 12-lead EKG performed to compare with the pre-MRI 12-lead EKG. The patient's symptoms will be

CONFIDENTIAL

This material is the property of Stanford University. Do not disclose or use except as authorized in writing by the study sponsor

reassessed 1 hour after infusion of the EVP1001-1 contrast. A differential and serum chemistry profile (with liver function test) will be performed within a month prior to administration of EVP1001-1 and within 24 hours post EVP1001-1. Adverse events (AEs) and discomforts will be recorded until discharge from the imaging center. At the 24 hour follow-up, the subject will be evaluated by telephone to determine if any AEs occurred from the time the subject left the imaging center. The subjects will have a contact number to report any AEs or to ask questions. Any clinically relevant changes from baseline in vital signs, ECG rhythm, clinical chemistries or physical condition and all AEs will be followed until resolution or until the outcome is known. Injection-associated discomforts will be recorded during administration and until imaging is completed. Primary efficacy will be based on determining whether the heart is normal or abnormal and if abnormal whether there is an infarction, ischemia or both. This provides the basis for calculating sensitivity, specificity, accuracy and predictive values. In addition, the location, size, conspicuity and associated confidence for any disease will be recorded.

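### QT/QTc change is to be attributed to EVP1001-1, but the two scheduled 12-lead ECGs bracket both contrast agents and possibly the premedication, and no QT reading between the agents is defined

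*Combined protocol and SAP*

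**What the plan says.** Section 3.2 (Primary Study Endpoints) makes QT/QTc part of the safety assessment and ties it to one agent: "Effects, if any, of EVP1001-1 on QT/QTc intervals will be determined by comparing the intervals before and after EVP1001-1 across the full HR range", with QT corrected for RR individually in each patient. It gives no time points, lead source or reading method.

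The ECG schedule is in section 3.1, under Parameters to be Measured: "A standard 12-lead EKG will be performed both before and after the MR study to assure no significant EKG changes have occurred". The same paragraph later says "After the study, the patient will have another standard 12-lead EKG performed to compare with the pre-MRI 12-lead EKG". It also provides for monitoring: "There will be a 5-minute post administration observation interval outside the scanner", followed directly by "The patient will also have continuous EKG monitoring during this time".

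Heart rate and blood pressure have a detailed series: "BP and HR will be measured every 2 minutes until 10 minutes post EVP1001-1 contrast infusion", then every 5 minutes to the end of MEMRI and every 10 minutes to the end of DEMRI. QT does not appear in that series.

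Section 3.1 also sets the order of drugs. Ondansetron is taken from 30 minutes before the scan, and metoprolol is given to patients who meet the heart-rate criteria. Then "EVP1001-1 will then be administered approximately 15 minutes into the scan", and afterwards "Following MEMRI, delayed-enhanced MRI(DEMRI)is performed using 0.2mmol/kg gadolinium". Section 4.3 describes the study as open-label and baseline-controlled.

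**The concern.** With no concurrent control group, the only thing that can link a QT change to EVP1001-1 is the timing of the readings relative to each drug given in the session. The endpoint promises a contrast around EVP1001-1. The 12-lead schedule supplies a contrast around the whole MR study, which contains two contrast agents, and possibly around the premedication too.

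Section 1.1 gives QTc and PR prolongation as one of the historical obstacles to intravenous manganese, so the sponsor has reason to want a clear answer. If the 12-lead pair is used as scheduled, a change could not be assigned to EVP1001-1, and an absence of change would describe only the state at the end of the session. Analysis cannot repair this afterwards if no suitable reading was taken.

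**Working it through.** The plan gives no sample size, power or threshold for QT/QTc, so there is no figure to reproduce. Two checks apply.

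**1. What the 12-lead difference measures**

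Write each QT reading (after rate correction) as

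QT = a + p·P + e·E + g·G,

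where P, E and G are 1 once premedication, EVP1001-1 and gadolinium respectively have been given, and 0 before. The target is e. An agent may have no effect (p or g equal to 0); the question is whether the schedule can tell.

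| Readings available | Difference obtained | Rank (of 4) | e estimable? |
|---|---|---|---|
| Baseline before premedication; final 12-lead | p + e + g | 2 | No |
| Baseline after premedication; final 12-lead | e + g | 2 | No |
| Baseline before premedication; reading between agents; final 12-lead | between − baseline = p + e | 3 | No |
| Baseline after premedication; reading between agents; final 12-lead | between − baseline = e | 3 | Yes |

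The first two rows are the two ways to read the pre-MRI 12-lead, because the text does not place it relative to ondansetron or metoprolol. The third row shows that adding a reading between the agents is not enough by itself: the baseline must also follow the premedication. Even the last row assumes that the premedication effect and spontaneous drift are stable between the two readings.

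**2. When the readings fall**

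- Scan length: about 1.5 h = 90 min per exam (Study Summary). Dose: about 15 min into the scan (3.1).
- Final 12-lead, if 1.5 h covers MEMRI and DEMRI together and the tracing is taken straight after: 90 − 15 = 75 min after dosing.
- Pre-MRI 12-lead, if taken before ondansetron: at least 30 + 15 = 45 min before dosing.
- Scheduled HR/BP readings in the first 10 min after dosing: 10 / 2 = 5.
- QT readings defined in the available text between EVP1001-1 and gadolinium: 0.

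On these inputs the first defined post-dose QT reading comes at about 75 minutes, after both agents, while heart rate already has five readings within 10 minutes.

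**The case against.** The strongest reply is that section 3.2 never says the QT comparison uses the 12-leads. The schedule gives those tracings a general checking role. A comparison over each patient's heart-rate range, with individual correction, could hardly rest on two tracings, so it may point to the continuous EKG. Section 3.1 also says subjects are monitored closely from before ondansetron until discharge, which favours a broad reading of the monitoring sentence. This stands in part: the table above models only the 12-leads, and its result applies only to them. But the section 3.1 sentence names no ECG, and no QT reading, lead set or window is defined for the continuous EKG. The closing words of "The patient will also have continuous EKG monitoring during this time" may cover the whole session or only the 5-minute interval mentioned just before, and that interval is not placed relative to gadolinium.

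Second, the Study Procedures Flowchart listed in section 14 was not available and may give ECG times. The count of zero is therefore provisional.

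Third, earlier human data were reassuring (sections 1.1 and 1.5), and section 4.2 excludes a history of torsades and QTc above 470 msec. That bears on how likely a problem is, not on whether the comparison can attribute one.

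Some stronger readings are tempting but unsupported:

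- *Gadolinium, ondansetron or metoprolol will distort QT here.* The documents give no figure for this. The point is only that the schedule cannot separate them.
- *The late ECG is uninformative because the drug has left the blood.* Clearance from blood is not clearance from heart muscle, and section 1.1 says myocardial enhancement persists.
- *The trial is the first use in patients with low EF.* The completed six-patient study had a mean LVEF of 32%.

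**Conclusion.** The point holds for the 12-lead pair. As scheduled in the available text, its difference equals the EVP1001-1 effect plus the gadolinium effect, plus the premedication effect if the baseline precedes it, and cannot be attributed to EVP1001-1 alone. A normal final tracing does not exclude an earlier, transient change. That the second 12-lead follows gadolinium is inferred from the MEMRI-then-DEMRI order and from its timing after the study; no sentence says so outright. The figure of about 75 minutes assumes that one 1.5-hour session covers both acquisitions.

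The documents do not support saying that QT will go unmeasured between the agents: the continuous EKG could supply it and the flowchart might specify it. Nor is any QT effect in milliseconds claimed. The defect is an attribution stated in 3.2 that the defined readings do not deliver. It should be corrected while the readings can still be specified.

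**What to change.** 1. In 3.1 and 3.2, name the source of the QT values and define at least one QT/RR reading after EVP1001-1 and before gadolinium. Take it from the continuous EKG already planned, timed with the scheduled HR/BP readings, or in the 5-minute interval outside the scanner if that precedes gadolinium. State the period that continuous monitoring covers.
2. Take the QT baseline after any premedication and before EVP1001-1. Use the planned pre-MRI 12-lead or the continuous EKG, matching the lead source of the post-dose reading.
3. Report the end-of-study 12-lead as a reading after both agents, and do not attribute its change to EVP1001-1 alone. This is also the fallback if in-scanner tracings cannot be read for QT.
4. If the flowchart already gives these times, cite it in 3.1.

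The cost is some additional ECG reading and a weaker claim from the final 12-lead. In-scanner tracing quality may limit what can be read, in which case a usable reading between the agents would have to come from outside the scanner. If continuous monitoring is now meant only for the 5-minute interval, recording would need to start before the dose whenever it is to supply the baseline. No extra visits or patients are needed, and drug administration is unchanged.

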#### Beta Blocker Administration Protocol

PROTOCOL	PARAMETER(s)	ACTION(s)
Assess whether $\beta$ -blockers are necessary	If pulse is < 65 bpm and regular or if pulse is < 60 bpm and irregular  If pulse is > 65 bpm or if pulse is > 60 bpm and irregular	A $\beta$ -blocker is not given  Screen for contraindications for giving $\beta$ -blocker
Screen for contraindications for $\beta$ -blockers	If any of the following conditions exist: Heart rate, < 60 bpm Systolic blood pressure, < 100 mm Hg Decompensated cardiac failure Allergy to $\beta$ -blocker Asthma or COPD on $\beta$ 2-agonist inhaler Active bronchospasm Second- or third-degree atrioventricular block  If the above conditions are absent	A $\beta$ -blocker is not given  Oral metoprolol is given
Administer metoprolol	If giving oral metoprolol,	One 50-mg dose of metoprolol is given orally and patient is monitored over 1 hr, during which heart rate is checked every 15 min. If heart rate remains elevated, perform practice breath-hold. If heart rate still remains elevated, give IV metoprolol
	If giving IV metoprolol	Two 2.5-mg doses of metoprolol are given 5 min apart; then, two doses of 5 mg each are given 5 min apart. Total maximum dose, 15 mg. Blood pressure and heart rate are checked before each IV dose
Administer postprocedure care	If only one dose of oral metoprolol is given	No monitoring necessary, patient can leave department after study
	If IV metoprolol is given	The patient is observed for 30 min
	If heart rate drops to < 45 bpm	Consideration is given to administering atropine
	If bronchospasm occurs	A $\beta$ -agonist inhaler is given

Note—bpm = beats per minute, COPD = chronic obstructive pulmonary disease.

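### The individual QT-RR correction over each patient's full heart-rate range, set out under the primary endpoints, is not supported by the ECG data that the protocol specifies

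*Combined protocol and SAP*

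**What the plan says.** Section 3.2 (Primary Study Endpoints) lists safety among the key endpoints. For QT/QTc it commits to "comparing the intervals before and after EVP1001-1 across the full HR range for each patient, including use of individual correction of QT by RR".

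The ECG data are described elsewhere:

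- Section 3.1 (General Design) includes an ECG in the entry assessment: "vital signs, electrocardiogram (ECG), evaluation of the major organ systems, hematology, serum chemistries".
- Parameters to be Measured states: "A standard 12-lead EKG will be performed both before and after the MR study to assure no significant EKG changes have occurred". It adds that afterwards "the patient will have another standard 12-lead EKG performed to compare with the pre-MRI 12-lead EKG". It gives no replicates, strip length or clock times.
- The same text states: "The patient will also have continuous EKG monitoring during this time". It does not define the period, the leads, whether the trace is stored, or whether QT is read from it.
- The Beta Blocker Administration Protocol gives metoprolol only above a pulse threshold. When the oral route is used, "One 50-mg dose of metoprolol is given orally". Section 3.1 also gives ondansetron by mouth 30 minutes before the scan. The pre-MR ECG is not timed relative to either drug.

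Section 7.2 (Statistical Methods) gives no QT method. Sections 4.3 and 8.2 refer to exercise tests and to stress before dosing, but neither appears in the procedures of section 3.1.

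**The concern.** An individual correction estimates each patient's own QT-RR relation from drug-free readings at several heart rates, then uses it to put the post-dose reading on a common footing. It needs enough drug-free pairs and enough spread in RR. The schedule appears to provide neither.

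The question is central to safety. Sections 1.1 and 1.4 name PR and QTc prolongation among the reasons why intravenous manganese was not at first usable in humans. If the stated analysis cannot be carried out, the correction will be chosen once the tracings are in hand, and the apparent QTc change can depend on that choice. In addition, metoprolol is given to slow the heart. A pre-MR tracing taken before it and a post-MR tracing taken after it would mix the effect of premedication with that of EVP1001-1.

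**Working it through.** The plan gives no numeric figure for the QT analysis, so there is none to reproduce. The check asks what the scheduled ECGs can identify, then how much the answer depends on what they leave unknown.

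**1. Identifiability.** For one patient write QT = a + b·RR + d·post, where b is the patient's slope and d the drug effect.

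- One pair before and one after: subtracting gives QT_post - QT_pre = b·(RR_post - RR_pre) + d. This is one equation in two unknowns (design rank 2 for 3 parameters). The drug-free slope alone has rank 1 of 2.
- Adding the screening ECG: b = (QT_pre - QT_screen)/(RR_pre - RR_screen), and d follows if the two RR values differ. The rank is 3 of 3 with 3 - 3 = 0 residual degrees of freedom, so a line can be drawn but without an error estimate.

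**2. Range of RR.** RR in ms is 60,000/heart rate: 923 ms at 65 bpm and 1,000 ms at 60 bpm. The two thresholds in the beta-blocker table are therefore 1,000 - 923 = 77 ms apart. Patients above the threshold are slowed, and those below it already have a low resting rate. No scheduled procedure produces a wide range.

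**3. Using beats within a tracing.** A strip holds several beats, so a slope can be fitted in principle. SE(b) = σ/(SD_RR·√(n-1)), and the 95% half-width in corrected QT over a 200 ms RR shift is 1.96·200·SE(b). SD_RR (20 to 60 ms), σ (QT error, 3 to 10 ms) and both beat counts are assumptions.

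| Data | SE(b), best to worst case | Half-width over 200 ms |
|---|---|---|
| 10 beats | 3/(60·3) = 0.017 to 10/(20·3) = 0.167 | 6.5 to 65.3 ms |
| 300 beats (5 min at 60 bpm) | 3/(60·√299) = 0.003 to 10/(20·√299) = 0.029 | 1.1 to 11.3 ms |

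A single strip is too imprecise in most of this range. Five analysable drug-free minutes could support a slope, but only within the RR values observed.

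**4. What an unknown exponent leaves open (illustration only).** Take QTc = QT/RR^β with RR in seconds. QT values, β and the 75 bpm rate are assumed.

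| Pre to post | β = 0.2 | β = 1/3 | β = 0.5 | Spread |
|---|---|---|---|---|
| 75 to 60 bpm, QT 380 to 400 ms | +2.7 | -9.3 | -24.9 | 27.6 ms |
| 65 to 60 bpm, QT 390 to 400 ms | +3.7 | -0.5 | -5.9 | 9.6 ms |

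For example, at β = 0.5 in the first row: 400/1.0^0.5 - 380/0.8^0.5 = 400 - 424.9 = -24.9 ms. The sign of the change can depend on the exponent. The spread is smaller when the two tracings are taken at similar rates, which is why the timing of the baseline matters.

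**The case against.** The strongest reply is that the protocol does not limit itself to two tracings. There is a screening ECG, and the continuous monitoring is loosely worded. Its period could be the short observation interval after dosing or the whole session. Subjects are watched from before ondansetron, and EVP1001-1 is given about 15 minutes into the scan, so a pre-dose trace is not ruled out. If that trace were stored at diagnostic quality, a slope within the resting range could be fitted. Section 14 also lists a procedures flowchart, which I have not seen.

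This stands as far as it goes. A reader might infer that the individual correction is impossible to compute, and the documents do not support that. They leave unspecified the data it would need. The reply still does not rescue the wording of section 3.2: no drug-free window, recording or QT reading is stated, and a resting trace would not cover a full heart-rate range.

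Two further limits are fair. Metoprolol is conditional, so it does not hold the rate down in every patient. And a patient with paroxysmal atrial fibrillation may be in sinus rhythm when recorded, so the irregular-RR problem belongs to the rhythm at recording, not to the diagnosis.

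The references to exercise and stress in sections 4.3 and 8.2 might be read as the missing source of heart-rate range. They are not in section 3.1 or Parameters to be Measured, so they contradict the schedule and must be reconciled with it.

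**Conclusion.** The point holds: the specified ECG data do not support the QT analysis stated in section 3.2. With one pair before and one after, slope and drug effect are not identifiable. With the screening ECG there are zero residual degrees of freedom. No scheduled step yields the heart-rate range that the wording requires. This is more than missing detail, because the analysis that is named does not match the data that are named.

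These conclusions rest on the schedule as written and a linear QT-RR model. The millisecond figures rest on assumed QT values, exponents, beat counts and measurement error. A reader might take the 9.6 to 27.6 ms spreads as the bias to expect, or as larger than any drug effect. Neither follows: the plan names no correction formula and gives no QT effect size, and sections 1.1, 1.4 and 1.5 report no QTc prolongation and no consistent drug-related QT change so far. The figures show only that a correction chosen after the data are seen can move the result.

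**What to change.** 1. In section 3.2, replace the individual correction with one fixed, pre-specified formula (for example Fridericia), averaged over several beats. State the number of beats for patients in atrial fibrillation at the time of recording. Delete the reference to the full heart-rate range.
2. In Parameters to be Measured, take the already scheduled pre-MR 12-lead after premedication and before the patient enters the scanner, and record its time and rhythm. A baseline immediately before EVP1001-1 would fall inside the scan, where no 12-lead is scheduled.
3. Show QT/QTc results separately for sinus rhythm and atrial fibrillation.
4. Reconcile the exercise and stress references in sections 4.3 and 8.2 with section 3.1.

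The cost is a wording change, a small scheduling change and a less individualised correction. A fixed formula will still be wrong for a patient whose own exponent differs. The later baseline limits that error by reducing the rate difference between tracings, although premedication effects may still be changing during the scan. No extra tracing is needed.

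If the sponsor prefers to keep an individual correction, the protocol would have to specify stored pre-dose continuous or replicate ECGs, a minimum number of QT-RR pairs and a rule for atrial fibrillation. It would also have to confine the claim to the observed RR range. That costs more in recording and reading.

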
All components of EVP are USP and are approved for use as drugs in man, orally and/or intravenously. A summary of the Phase I safety and PK (pharmacokinetics) study are provided below.

The Phase I study evaluated the safety and tolerance of EVP in humans, with special emphasis on cardiovascular safety, and assessed its PK profile. Overall, EVP was found to be safe at all doses. There were no serious adverse events (SAE) or any events requiring medical treatment. Of special importance, no signs of cardiac depression were reported. In addition, there was no observation of prolongation of the QTc or PR intervals or other ECG-changes that had previously been reported in animals for Mn. There were no changes in hematology, serum biochemistry (including liver function tests), coagulation parameters nor in temperature, respiratory rate or blood oxygen levels.

Transient increases in HR and BP were seen. These, for the most part, reflected transient changes within the normal reference range. There was no obvious dose-relationship for these responses, although their duration and magnitude were greater for the 5-minute than for the 1-minute dose administrations.

Other AEs were reported, almost all which were regarded as of mild or moderate intensity. Almost all events occurred during or immediately after dosing and resolved within minutes. Over 83% of the AEs occurred during dosing and over 93% occurred within one minute of dosing. Nearly one-third of all events resolved within one minute from dosing, over 80% within 5 minutes, and 94% resolved within ½ hour. The most frequent types of AEs were injection-associated discomforts (warmth, flushing, cold, pressure, injection site changes), increased HR/BP, gastrointestinal disturbances (discomforts, nausea, vomiting, diarrhea), lacrimation and headache. Although gastrointestinal disturbances, such as nausea and occasional vomiting, resolved rapidly without treatment, these bothersome events may be avoidable through the use of a standard anti-emetic. This proved to be beneficial in humans and also in high-dose animal studies.

The PK profile reflected what was known for Mn in humans (based on reported radiotracer Mn studies), with a primary blood half-life under 1 minute, and less than 1% of the dose remained in the blood by 30 minutes after dosing. The performance

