#### **4.3 Subject Recruitment and Screening**

This is an open-label, baseline-controlled study to be conducted. Adult male or non-pregnant female patients who have been referred for evaluation of cardiomyopathy and atrial fibrillation and patients who have received stem cell therapy related to these indications will be recruited. An initial cohort study of 6 patients to conduct safety evaluation was conducted before proceeding with 120 additional patients. In the initial cohort, a patient was dosed based on the Phase 1 and 2 clinical trial data evaluation completed by Eagle Vision Pharmaceutical, Inc. Subjects were excluded if they had received an investigational device within 30 days prior to administration of EVP1001-1; had a history of drug abuse or alcoholism; were taking a digitalis preparation; had a history of torsades; had NYHA Grade IV heart failure; had abnormal liver function tests or a history of liver disease; had uncontrolled hypertension; had abnormal calcium, potassium or hemoglobin values at baseline; if they develop a cardiac arrhythmia prior to or during either of the exercise tests-- EVP1001-1 was not administered. The same parameters will apply to the new group of subjects.

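### With no fixed baseline time and no split by metoprolol use, the pre/post heart-rate and blood-pressure comparison can mix the effects of EVP1001-1 and metoprolol

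*Combined protocol and SAP*

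**What the plan says.** **The comparison.** Section 3.2 (Primary Study Endpoints) makes safety and tolerance of EVP1001-1 a key endpoint. It states: "Pre- and post-dose results will be compared for vital signs, clinical laboratory parameters, ECG parameters and hemodynamic parameters". The purpose is to pick up changes in individual patients and shifts in the group as a whole. On the analysis set it says: "All subjects who receive EVP1001-1 will be included in the analyses". Section 4.3 describes the control: "This is an open-label, baseline-controlled study to be conducted".

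**Attribution to the agent.** For repolarisation, section 3.2 says: "Effects, if any, of EVP1001-1 on QT/QTc intervals will be determined by comparing the intervals before and after EVP1001-1". It adds that QT will be corrected by RR individually and examined over each patient's HR range.

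**Metoprolol.** Section 3.1 says that, for image quality, "if the participant heart rate is greater than 65 bpm and regular rhythm, metoprolol will be given". The Beta Blocker Administration Protocol table gives the sequence: "One 50-mg dose of metoprolol is given orally and patient is monitored over 1 hr". If the rate stays high, IV dosing follows: "Two 2.5-mg doses of metoprolol are given 5 min apart; then, two doses of 5 mg each are given 5 min apart".

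**Timing of readings.** Under Parameters to be Measured (section 3.1), one baseline BP and HR is taken ahead of the study. Readings then follow every 2 minutes for 10 minutes after EVP1001-1, and less often after that. A 12-lead ECG is done before and after the MR study. None of the pre-dose readings is placed before or after metoprolol.

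**Expected signal.** Section 1.4 reports from Phase I: "Transient increases in HR and BP were seen".

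**Methods.** Section 7.2 lists a t-test of MEMRI against DEMRI and a Pearson correlation. It gives no method for the safety changes and does not mention metoprolol.

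**The concern.** In a baseline-controlled design, any other influence acting between the baseline and post-dose readings is counted as an effect of the study agent. Metoprolol is given on the scan day in order to lower heart rate, so it acts against the signal Phase I points to. Who receives it is decided by heart rate, one of the variables being assessed. The analysis as written neither separates the two drugs nor fixes a baseline that would do so.

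What is at stake is how the haemodynamic safety result is read. A real rise after EVP1001-1 could be masked. Alternatively, a fall caused by metoprolol could look like the cardiac depression that section 1.4 singles out as an important concern with manganese. Either way, the size of the distortion would depend on how many enrolled patients happened to need metoprolol.

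**Working it through.** The plan states no sample size, test or effect size for the HR/BP/ECG comparison, so there is no figure to reproduce. The check is the order of events, then an illustration on stated assumptions.

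**1. Order of events.** The metoprolol table has an hour of observation after the oral dose and 5-minute IV steps. Section 3.1 places EVP1001-1 about 15 minutes into the scan. Metoprolol therefore comes before EVP1001-1, although the exact interval is not stated. Baseline HR/BP could be taken before or after metoprolol; both fit the text.

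**2. If baseline precedes metoprolol's effect.** Let E be the true EVP1001-1 change, p the share given metoprolol, and d the metoprolol fall between baseline and post-dose readings. Taking the two effects as additive:

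mean change over all patients = E - p x d

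None of E, p or d is in the documents. With assumed E = 8 bpm:

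| p | d = 5 | d = 10 | d = 15 |
|---|---|---|---|
| 0.3 | +6.5 | +5.0 | +3.5 |
| 0.5 | +5.5 | +3.0 | +0.5 |
| 0.7 | +4.5 | +1.0 | -2.5 |

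With p from 0.25 to 0.75 and d from 5 to 15:
- E = 5 gives 5 - 0.25 x 5 = +3.75 down to 5 - 0.75 x 15 = -6.25.
- E = 10 gives 10 - 0.25 x 5 = +8.75 down to 10 - 0.75 x 15 = -1.25.

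The result can be reduced, cancelled or reversed.

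**3. If baseline follows metoprolol.** Then d shrinks to whatever fall is still developing (r), plus any loss of response in a beta-blocked patient (b): mean change = E - p x (r + b). The documents give no size for r or b, so the table above does not apply.

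**4. How many patients are affected.** Assume resting HR has mean 65-75 bpm and SD 10. Then 50-84% exceed 65 bpm. Of the 50 patients in the Study Summary, that leaves 50 x 0.16 = 8 to 50 x 0.50 = 25 untreated.

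**5. Why the baseline and the split belong together.** If the reading that triggers metoprolol also serves as baseline, selection alone creates change. With a repeat correlation of 0.6-0.8 and the same HR assumptions, regression to the mean in the treated group is about -0.6 to -3.2 bpm. Over all patients regression to the mean averages zero, so the untreated group must rise by p/(1 - p) times that amount:
- At mean 65: 0.50/0.50 x 1.60 = +1.6 to 0.50/0.50 x 3.19 = +3.2.
- At mean 75: 0.84/0.16 x 0.58 = +3.0 to 0.84/0.16 x 1.15 = +6.0.

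A split on the trigger reading would therefore exaggerate the rise in untreated patients. A separate reading just before EVP1001-1 largely avoids this.

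**6. Which parameters.** HR and BP have no correction for metoprolol. QT/QTc has individual RR correction, which deals with the part of the change that runs through heart rate. Other ECG parameters, such as PR, have no such protection.

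**The case against.** The strongest objection is that the baseline may well follow metoprolol. Section 3.2 speaks of pre- and post-dose, and the dose is EVP1001-1. The metoprolol table requires HR checks during the hour after the oral dose, and BP and HR before each IV dose, so readings after at least some metoprolol will exist. This stands: the numerical range holds only for a pre-metoprolol baseline. It does not settle the matter, because the one baseline the protocol defines is not tied to metoprolol.

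It also stands that including all dosed patients defines an analysis set and does not forbid a breakdown. No pooled test on HR or BP is specified, individual changes will be examined, and frequent post-dose readings will show short-lived rises. But individual changes carry the same mixture of effects, and no breakdown is planned.

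Four stronger readings are tempting and are not supported:

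- A reader might infer that the bias always runs towards no change. It can reverse: at E = 8 and d = 15 a treated patient changes by 8 - 15 = -7 bpm.
- A reader might infer that faster patients, many of them in atrial fibrillation, will look the most stable. That same -7 is nearly as large as the untreated +8, and the documents give no share for atrial fibrillation.
- A reader might infer that QT/QTc is compromised to the same degree as HR and BP. The RR correction argues against that, and selection is on heart rate, not on BP or ECG intervals.
- A reader might infer that patients without metoprolol show EVP1001-1 alone. Everyone takes ondansetron under section 3.1, and section 4.2 does not exclude existing beta-blocker use.

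**Conclusion.** The point holds in conditional form. As written, the plan lets the HR and BP change mix EVP1001-1 with metoprolol, because the only control is a baseline whose timing relative to metoprolol is open and no split by metoprolol is planned. With a pre-metoprolol baseline, and assuming a true rise of 8 bpm, 30-70% treated and a 5-15 bpm fall, the mean change over all patients would be +6.5 to -2.5 bpm. These inputs are assumptions, not figures from the documents. With a post-metoprolol baseline the distortion is smaller and cannot be sized from the documents. QT/QTc is partly protected.

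This does not undermine the safety assessment as a whole, which also rests on adverse events, discomforts and laboratory results. It is a cheap improvement to one part of a key endpoint.

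**What to change.** In sections 3.1 and 3.2:

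1. Define baseline HR and BP, and ECG where available, as the last reading after any metoprolol and just before EVP1001-1. Record metoprolol dose, route and time.
2. Report HR, BP and ECG-interval changes overall and separately for no metoprolol, oral only, and IV metoprolol.
3. Base statements about EVP1001-1 without study metoprolol on the untreated group. Note that this group is selected for low heart rate, takes ondansetron and may include patients on existing beta-blockers. Describe the other groups as EVP1001-1 after metoprolol.
4. Reconcile the irregular-rhythm heart-rate cut-offs, which are 65 bpm in the section 3.1 text and 60 bpm in the table, because they determine who falls in which group. The metoprolol rules themselves are not questioned here.

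The cost is a few sentences and possibly one extra set of readings; metoprolol is given under the protocol, so its use should be in the study record. The downside is precision. With 8-25 untreated patients out of 50 (on the assumptions above), and the same SD, intervals in that group would be about sqrt(50/25) = 1.4 to sqrt(50/8) = 2.5 times as wide as for all 50.
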